7.2.5. Definition of Responder at Week 52 and Week 104/EOT

A DYS responder is defined separately for Week 52 and Week 104/EOT. A DYS responder is defined as a patient with data that satisfies each of the following:

- had a reduction in average DYS NRS pain score from pivotal phase 3 study baseline of at least 2.8 points, or had a DYS NRS pain score ≤ 0.1 at Week 52 or Week 104/EOT if the pivotal phase 3 study baseline DYS pain score was less than 2.8;
- did not have an increase in the use of rescue analgesic medications for endometriosis-associated pain compared with pivotal phase 3 study baseline use (Table 14) at Week 52 or Week 104/EOT.

An NMPP responder is defined separately for Week 52 and Week 104/EOT. An NMPP responder is defined as a patient with data that satisfies each of the following:

- had a reduction in average NMPP NRS pain score from baseline of at least 2.1 points, or had a NMPP NRS pain score ≤ 0.1 at Week 52 or Week 104/EOT if the pivotal phase 3 study baseline NMPP pain score was less than 2.1;
- did not have an increase in the use of rescue analgesic medications for endometriosis-associated pain compared with pivotal phase 3 study baseline use (Table 15) at Week 52 or Week 104/EOT.

The reduction from baseline in DYS or NMPP pain scores at Week 52, or Week 104/EOT will be calculated separately as the absolute difference between the respective average pain score at Week 52, or Week 104/EOT and the average pain score at pivotal phase 3 study baseline.

According to the description given above, patients who have an average baseline DYS or NMPP score smaller than the corresponding meaningful change threshold may still be classified as a responder if their average pain score at Week 52, or Week 104/EOT is no more than 0.1. This condition is strict and can only be met when nearly all daily pain scores from the assessment period are 0, with the very few remaining daily pain score(s) being minimal.

The responder status for DYS or NMPP at Week 52, Week 104/EOT will be assessed based on the reduction from pivotal phase 3 study baseline in average pain scores (ie, whether there is a reduction of at least the meaningful change threshold as described above), change from pivotal phase 3 study baseline in use of rescue analgesic medications, compliance with eDiary entry over the Week 52, Week 104/EOT pain assessment period, and menstruation status per the eCRF.

Further details of the derivation of responder status are given in Section 7.2.6.

7.2.6. Derivation of Responder Status at Week 52, Week 104/EOT and Missing Data Handling Rules

For the primary efficacy analysis, both primary endpoints will incorporate the missing data handling rules at Week 52, Week 104/EOT as follows (Table 14, Table 15 and Figure 2):

- For patients missing eDiary for all visits in the extension study, their Baseline/Week 24 responder status from the pivotal phase 3 study will be carried over as their responder status to Week 52, Week 104/EOT.
- For patients who have any pain score entries in eDiary in the extension study, responder status for DYS and NMPP will be derived as follows:
 - For DYS, the responder status will be defined using the following rules taking analgesic use into consideration (Table 14):
 - If there are at least 2 days of DYS NRS scores reported in the eDiary, then the average will be calculated and used in the assessment of the DYS responder status. Requiring a minimum of 2 days of DYS NRS scores is considered reasonable since a typical menstrual cycle has bleeding days ranging from 3 to 7 days.
 - If there are < 2 days of NRS scores for DYS reported in the eDiary, then the following scenarios will be considered:
 - If no DYS scores are reported in the eDiary, then the data collected on the menstruation eCRF will be considered as follows:
 - If no menstruation is reported on the eCRF, then the average DYS score will be set as 0;
 - Otherwise, if any menstruation days are reported on the eCRF, then the average DYS score will be set as missing and will be imputed using a mixed-effects model.

- If only one DYS score is reported in the eDiary, then the data collected on the menstruation eCRF will be considered as follows:
 - If no more than one menstruation day is reported on the eCRF, then the observed DYS score will be taken as the average DYS score;
 - If more than one menstruation day is reported on the eCRF, then the average DYS score will be considered missing and will be imputed using a mixed-effects model.
- For NMPP, the responder status will be defined using the following rules, taking analgesic use into consideration (Table 15):
 - If there are at least 14 days of scores for NMPP reported in the eDiary, then the average NMPP score will be used in the assessment of the NMPP responder status. Requiring minimum 14 days of NMPP scores is considered reasonable since this corresponds to at least half of the non-menstrual days from a typical 28-day menstrual cycle.
 - If there are less than 14 days of NMPP scores in the eDiary, then the average NMPP score will be considered missing and will be imputed using predicted values from a mixed-effects model.

Table 14: Missing Data Handling Rules for Average Dysmenorrhea NRS Score at Week 52, Week 104/ EOT

Number of Days with DYS Scores Reported in eDiary	Menstruation Status per eCRF	Average DYS Score Status	Responder Status ^a
Missing all eDiary data during extension study			
n/a	n/a	n/a	Baseline/Week 24 responder status from pivotal phase 3 study
Having at least one eDiary data during extension study			
≥ 2 days	n/a	Observed	Based on observed change from baseline and analgesic use
1 day	No more than 1 menstruation day reported	Observed	Based on observed change from baseline and analgesic use
	More than 1 menstruation day reported	Missing (to be imputed from mixed-effects model)	Based on imputed change from baseline and analgesic use
0 days	No menstruation days reported	Assigned as 0	Based on change from baseline and analgesic use
	At least 1 menstruation day reported	Missing (to be imputed from mixed-effects model)	Based on imputed change from baseline and analgesic use

Abbreviations: eCRF = electronic case report form; eDiary = electronic diary; n/a = not applicable.

^a Determined by comparing the observed (or imputed) change from baseline to the responder threshold and by examination of change from baseline in analgesic use.

[figure not shown]
Table 15: Missing Data Handling Rules for Average Non-Menstrual Pelvic Pain NRS Score at Week 52, Week 104/EOT

Number of Days with NMPP Scores Reported in eDiary	Average NMPP Score Status	Responder Status ^a
Missing all eDiary data during extension study		
n/a	n/a	Baseline/Week 24 responder status from pivotal phase 3 study
At least one eDiary data during extension study		
≥ 14 days	Observed	Based on observed change from baseline and analgesic use
< 14 days	Missing (to be imputed from mixed-effects model)	Based on imputed change from baseline and analgesic use

Abbreviations: eDiary = electronic diary; n/a = not applicable; NMPP = non-menstrual pelvic pain.

^a Determined by comparing the observed (or imputed) change from baseline to the responder threshold and by examination of change from baseline in analgesic use.

Figure 2: Visual Depiction of the Missing Data Handling Rules and Determination of Responder Status for the Primary Efficacy Endpoints

Abbreviations: CRF = case report form; DYS = dysmenorrhea; EOT = end of treatment; NMPP = non-menstrual pelvic pain.

T represents the responder threshold (-2.8 for dysmenorrhea and -2.1 for NMPP) determined from the anchor-based analyses.

7.2.7. Mixed-Effects Model for Imputing Missing or Partially Missing Pain Scores at Week 52 and Week 104/EOT

For the primary analysis in the final analysis, patients with missing pain scores at Week 52, Week 104/EOT will be identified separately for DYS and NMPP, per the missing data handling rules described above. For imputing missing data for the primary analysis of each primary endpoint, a mixed-effects model approach will be used to derive predicted average pain scores,

as the mixed-effects approach may better describe the effects of a hormonal treatment (such as suppression of the hypothalamic-pituitary-ovarian axis by gonadotropin-releasing hormone (GnRH) receptor antagonists) than other imputation methods, such as multiple imputation.

Specifically, a mixed-effects model with repeated measures of average pain scores at multiple time points will be fitted to predict change in average pain scores from baseline (as a dependent variable) through the fixed-effects associated with covariates (ie, stratification factors of years since endometriosis diagnosis at pivotal phase 3 study baseline and geographic region, visit, treatment, treatment-by-visit interaction, pivotal phase 3 study baseline average NRS score,) and random effects (from the individual patients). Here treatment refers to pivotal Phase 3 pivotal phase 3 study treatment group. In this model, an unstructured variance-covariance matrix is assumed for each patient. If the mixed-effects model fails to converge, a first-order autoregressive variance-covariance matrix will be used. Multiple time points at Weeks 4, 8, 12, 16, 20, 24, 28, 32, 36, 40, 44, 48, 52, 65, 78, 91, 104 and 104/EOT will be used for the analyses.

Sample SAS code is provided below for illustration. The specification of type=UN implements unstructured variance-covariance matrix for an individual patient with multiple measures of average pain scores. If the model fails to converge, then variance-covariance matrix structure will be specified as first-order autoregressive (ie, AR(1)).

```
proc mixed data=NRS_dataset method=REML covtest;
class PID DXYRS REGION VISIT TRT;
model CHG_NRS = DXYRS REGION BASE VISIT TRT VISIT*TRT / s outp=emmi_mixed_p covb
outp=emmi_mixed_p covb;
repeated VISIT / type=UN subject=PID r;
lsmeans VISIT*TRT;
ods output SolutionF=mixparms CovB=mixcovb;
```

BASE is the pivotal phase 3 study baseline pain score; CHG_NRS is change in average pain score from pivotal phase 3 study baseline to Week 104/EOT as the dependent variable; DXYRS is a randomization stratification factor (years since endometriosis diagnosis: < 5 versus ≥ 5); PID is patient identification number; REGION is a randomization stratification factor (North America versus rest of world); TRT is pivotal phase 3 study treatment group (relugolix + E2/NETA, relugolix + delayed E2/NETA, placebo); VISIT is visit time point.

Applying this model over the observed longitudinal average NRS score data, the fixed-effects will be estimated and the relationship of change in average NRS scores from pivotal phase 3 study baseline with the covariates will be characterized by the fitted model. From the fitted model, the change in average NRS scores (whether missing or not) will be predicted for each patient at each visit and in a particular stratum. The imputed average NRS scores at Week 52 or Week 104/EOT will be obtained by adding the pivotal phase 3 study baseline average NRS scores to the difference.

Since the purpose of using the mixed-effects model is to impute the missing average NRS scores identified at Week 52 or Week 104/EOT as described above, the predicted average NRS scores from the model at the corresponding Week 52 or Week 104/EOT visit (at which the missing average NRS scores are identified) will be used in the determination of responder status. For patients without the need for imputation, their responder status will be derived based on the observed data according to the algorithms laid out in Figure 2.

This imputation approach is consistent with the definition of responder at Week 52, Week 104/EOT for the primary endpoints.

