Descriptive assessments of efficacy and safety will be made on data collected from the pivotal phase 3 study Baseline through Week 52, and from the pivotal phase 3 study Baseline through the end of the extension study (Week 104) on the extension study population, defined as patients who enrolled in MVT-601-3103 (i.e., who received at least one dose of study drug in the extension study), for the following treatment groups originally randomized in the pivotal phase 3 studies:

- Pivotal phase 3 relugolix + E2/NETA group: Randomized to 24 weeks of oral relugolix 40 mg once daily co-administered with 1 mg estradiol and 0.5 mg norethindrone acetate in the pivotal phase 3 study;
- Pivotal phase 3 relugolix + delayed E2/NETA group: Randomized to 12 weeks of oral relugolix 40 mg once daily followed by 12 weeks of oral relugolix 40 mg once daily co-administered with 1 mg estradiol and 0.5 mg norethindrone acetate in the pivotal phase 3 study;
- Pivotal phase 3 placebo group: Randomized to 24 weeks to placebo in the pivotal phase 3 study.

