Week 44	X ₁₁	(X ₁₁ - 34) to ≤ X ₁₁
Week 48	X ₁₂	(X ₁₂ - 34) to ≤ X ₁₂
Week 52	X ₁₃	(X ₁₃ - 34) to ≤ X ₁₃
Week 65 ^g	X ₁₄	(X ₁₄ - 56) to ≤ X ₁₄
Week 78 ^g	X ₁₅	(X ₁₅ - 56) to ≤ X ₁₅
Week 91 ^g	X ₁₆	(X ₁₆ - 48) to ≤ X ₁₆
Week 104 ^g	X ₁₇	(X ₁₇ - 51) to ≤ X ₁₇
Week104/EOT ^c	X ₁₇	Maximum [OLE start day ^c , (X ₁₇ - 34)] to ≤ X ₁₇ or PAP ^f

Abbreviation: EOT = end of treatment, OLE = open label extension.

Error! Reference source not found. Refer to **Error! Reference source not found.** Table 3 for target study day for Weeks 4, 8, 12, 16, 20, 24, 28, 32, 36, 40, 44, 48, 52, 65, 78, 91, 104 and safety Follow-Up.

^b The target study day for Week 24 is defined as date of last dose of randomized study treatment in pivotal phase 3 study. The Week 24 assessment period is defined as the 35 days up to and including the date of last dose of randomized study treatment in pivotal phase 3 study, which should occur on the day prior to the Week 24 visit.

^c OLE start day = day of first dose administered of extension study treatment.

^e The target study day for Week 104/EOT for purposes of visit window calculations is defined as date of last dose of study treatment in the extension study.

^f If the last 35 calendar days prior to and including date of last dose of study drug are not entirely within an eDiary collection period, then days of the pain assessment period (PAP) will be determined as follows: (1) if the date of last dose occurs during the eDiary collection period, the PAP will be the last 35 days which are counted during up to two eDiary collection periods immediately prior to and including date of last dose of study drug (2) if the date of last dose occurs outside of the eDiary collection period, the PAP will be the last 35 days which are counted during up to two eDiary collection period(s) immediately prior to but not including date of last dose of study drug.

^g: For Week 65, Week 78, Week 91 and Week 104, only data collected within eDiary cycles required by protocol is included in the analysis.

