35 calendar days immediately prior to and including the date of last dose of study drug;

- If the date of last dose occurs outside of the eDiary collection period or there are not 35 calendar days prior to the last dose of extension study drug from the eDiary collection period that includes the last dose, the PAP will be the last 35 days in the eDiary collection day on or prior to the last dose of study drug, from the last one or two eDiary collection periods.
- If the last 35 calendar days prior to and including date of last dose of study drug are not entirely within an eDiary collection period:
 - if the date of last dose occurs during the eDiary collection period, the PAP will be the last 35 days which are counted during up to two eDiary collection periods immediately prior to and including date of last dose of study drug
 - if the date of last dose occurs outside of the eDiary collection period, the PAP will be the last 35 days which are counted during up to two eDiary collection period(s) immediately prior to but not including date of last dose of study drug

Week 104/EOT analgesic use for pelvic pain is the average daily pill count as reported in the eDiary during the Week 104/EOT PAP. The average daily pill count will be calculated separately for Tier 1 and Tier 2 analgesics for Week 104/EOT.

NRS pain scores and analgesic use during PAP of each of other study weeks will be calculated for efficacy analysis by visit. Pain scores for DYS and NMPP are the averages of the respective eDiary pain scores reported during each individual PAP. Analgesic use for pelvic pain is the average daily pill count as reported in the eDiary during each individual PAP.

For Week 65, 78, 91 and 104, PAP is defined as the total days of ed diary collection period immediately prior to respective week. For Week 28 to Week 48, PAP is defined as the last 35 calendar days of extension study treatment immediately prior to respective week. For patients with extension study treatment duration less than 35 days, PAP is defined as the days between the first dose of extension study drug and date of last dose of extension study drug. **Definition of Increased Use of Analgesics**

The definition of increased analgesic use in pivotal phase 3 studies will be applied to this extension study. Protocol-specified analgesic medications for endometriosis-associated pain will be analyzed based on the following categories:

- Tier 1
 - Ibuprofen (200 mg)
- Tier 2:

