 - Tramadol (37.5 mg)/Paracetamol (325 mg)
 - Tramadol (50 mg)
 - Codeine (30 mg)
 - Codeine (30 mg)/Paracetamol (300 mg)
 - Codeine (30 mg)/Paracetamol (500 mg)

- Codeine (15 mg)/Paracetamol (500 mg)
- Hydrocodone (5 mg)/Paracetamol (325 mg)

The Tier 2 analgesics prescribed for use in the study was country specific. Patients will record their use of these medications in an eDiary every day until Week 52 and after Week 52, eDiary scores will be entered over four eDiary collection cycles on following schedules: Week 57 to the Week 65 visit, Week 71 to the Week 78 visit, Week 85 to the Week 91 visit, and Week 98 to the Week 104 visit. This will include the information on medication name, dosage, usage of medication (eg, for endometriosis-associated pelvic pain or not), and total number of pills taken. The percent change in analgesic use between the pivotal phase 3 study baseline and Week 52 will be calculated as absolute change in analgesic use from pivotal phase 3 study baseline to Week 52 divided by pivotal phase 3 study baseline analgesic use. The percent change in analgesic use between the pivotal phase 3 study baseline and Week 104/EOT will be calculated as absolute change in analgesic use from pivotal phase 3 study baseline to Week 104/EOT divided by pivotal phase 3 study baseline analgesic use. For the primary endpoints of DYS and NMPP, patients will be considered as non-responders if they have an increase in rescue analgesic use as specified in Table 13.

Table 13: Effect of Protocol-Specific Analgesic Medication Use for Endometriosis-Associated Pain on Responder Status at Week 52, Week 104/EOT

Analgesic Use for EAP at Pivotal phase 3 study Baseline	Tier 1 Analgesic Use for EAP	Tier 2 Analgesic Use for EAP	Analgesic Responder Status ^a
Missing all eDiary data during extension study			
n/a	n/a	n/a	Baseline/Week 24 analgesic responder status from pivotal phase 3 study
At least one eDiary data during extension study			
No analgesic use	Any use	OR Any use	Non-responder
	No use	AND No use	Responder
Used Tier 1 analgesic only	Use increased > 15% from baseline	AND No use or any use	Non-responder
	Any use or no use	AND Any use	
	Use stopped, decreased, or stable	AND No use	Responder
Used Tier 2 analgesic only	Any use or no use	AND Use increased > 15% from baseline	Non-responder
	Any use	AND Use is stable	
	No use	AND Use stopped, decreased, or stable	Responder
	Started use	AND Use stopped or decreased	

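### Women with no extension diary keep their pivotal Week 24 responder status at Week 52 and Week 104/EOT, so in the former placebo group outcomes on placebo are reported as long-term outcomes on relugolix + E2/NETA

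*SAP*

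**What the plan says.** Section 7.2.6 sets the missing-data rules for the primary analysis of both responder endpoints. Its first rule covers women without any extension eDiary: the Week 24 "responder status from the pivotal phase 3 study will be carried over as their responder status to Week 52, Week 104/EOT". Tables 14 (dysmenorrhea) and 15 (NMPP) enter the same result, "Baseline/Week 24 responder status from pivotal phase 3 study". Table 13, in Section 7.2.4, does so for the analgesic component under the row "Missing all eDiary data during extension study", with "Baseline/Week 24 analgesic responder status from pivotal phase 3 study". None of these places makes an exception by pivotal treatment group.

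Three other provisions matter:

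- Section 4.2.1: any amount of open-label drug puts a woman in the efficacy population. No diary data are needed.
- Section 1.1 defines the former placebo group: "Pivotal phase 3 placebo group: Randomized to 24 weeks to placebo in the pivotal phase 3 study".
- Section 4.3.8, Table 11, footnote b: "The Week 24 assessment period is defined as the 35 days up to and including the date of last dose of randomized study treatment".

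Section 7.2.1 makes the 7.2.6 rules part of the primary analysis and presents the rate with a 95% CI by pivotal group. The SAP plans no sensitivity analysis of the carry-over rule and no count of the women it covers.

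**The concern.** The primary objective is long-term efficacy of relugolix + E2/NETA to 52 and 104 weeks. A former placebo woman who took one open-label dose and made no diary entry can be reported as a Week 104 responder, or non-responder, on evidence collected entirely before her first relugolix tablet. In the relugolix + E2/NETA and delayed E2/NETA groups the carried status does come from the combination, but a 24-week finding then appears under 52- and 104-week labels.

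The rule also fits poorly with Section 7.2.5, which defines a responder as someone whose data meet both the pain and the analgesic criteria at the time point in question. These women have no eDiary data at either time point. At stake is what the headline rate means, above all in the placebo-to-relugolix row.

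**Working it through.** **Which treatment the carried status reflects.** The Week 24 window is 35 days ending on the last randomized dose.

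| Pivotal group | Treatment in the Week 24 window | Extension treatment |
|---|---|---|
| Relugolix + E2/NETA | combination | same combination |
| Delayed E2/NETA | combination (second 12 weeks = 84 days, longer than 35) | same combination |
| Placebo | placebo | combination, new at Week 24 |

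Only the placebo row crosses a change of treatment.

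**The plan's own figure.** Section 2.2 gives about 800 women as 67% of 1200. 0.67 × 1200 = 804 and 800/1200 = 66.7%, so it reproduces. There is no power calculation to check.

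**Inputs the SAP does not give (assumed).**

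- Group size n: 800/3 ≈ 267, taking equal groups.
- Share with no extension diary, m: 1-5%, or about 3 to 13 women per group.
- Week 24 placebo response, pP: 25-45%.
- Response among women with extension diary data, pR: 60-75%.

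**Formulas for the former placebo group.**

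- Carry-over: (1 − m)·pR + m·pP
- Non-responder imputation: (1 − m)·pR
- Diary-only: pR
- Carry-over minus non-responder imputation: m·pP
- Carry-over minus diary-only: m·(pP − pR)

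**Results.**

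- Against non-responder imputation: from 1% × 25% = +0.25 to 5% × 45% = +2.25 points.
- Against diary-only: from 1% × (45% − 60%) = −0.15 to 5% × (25% − 75%) = −2.50 points.
- Example with m = 5%, pP = 30%, pR = 75%: carry-over 71.25 + 1.50 = 72.75%; non-responder imputation 71.25%; diary-only 75.00%. About 13 × 0.30 ≈ 4 placebo responses are counted as long-term responses.
- The effect is linear in m: at m = 10% and pP = 30% it is +3.0 points against non-responder imputation.

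**Relugolix groups.** With an assumed Week 24 response of 60-75%, the difference from non-responder imputation runs from 1% × 60% = 0.60 to 5% × 75% = 3.75 points.

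**The case against.** The case for leaving the rule alone has real content.

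- **Scope.** Any extension pain entry moves a woman to the observed-data or mixed-model rules, and the diary is daily to Week 52. The set may be very small. On the assumptions above, 2.25 points is less than half the 95% CI half-width of about 5.2 points (1.96 × √(0.75 × 0.25/267)). This stands, and it limits the size of the problem.
- **Direction.** A reader might infer that the rule inflates the long-term rate. The documents do not support that as a general statement. Placebo non-response is carried too, so against a diary-only rate the former placebo figure falls whenever placebo response is below open-label response.
- **Change of treatment.** A reader might infer that every woman's carried status predates a change of treatment. That holds only for the placebo group.
- **Who these women are.** They might be taken for very early stoppers. The SAP does not say so.
- **Consistency.** Table 11 starts the Week 28, Week 32 and Week 104/EOT windows no earlier than the first extension dose. For exposure under 35 days, Section 7.2.4 says "PAP is defined as the days between the first dose of extension study drug and date of last dose of extension study drug", for Week 52 and for Weeks 28 to 48. These bounds apply to women with diary data and do not address women with none. The Section 7.2.7 imputation model is also fitted to pivotal visits, so it would be wrong to say that the SAP keeps pivotal data out. The difference is that the model has a treatment-by-visit term and can reflect change after Week 24, whereas carry-over assumes none.
- **Confidence interval.** Treating carried values as observed is common to any single imputation, including the one proposed here, so it is no separate argument.
- **Discontinuity.** Under non-responder imputation, one diary entry earns a model prediction and none earns a failure. That is so, but the present rule has a break at the same point.

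None of this explains why a status measured on placebo should stand as a Week 52 or Week 104 outcome on relugolix + E2/NETA.

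**Conclusion.** The point holds, within limits. As written, the rule reports placebo outcomes in the former placebo group, and Week 24 outcomes in the two relugolix groups, as Week 52 and Week 104/EOT results in the primary analysis, with no planned check. The defect lies in what the rate represents; its sign depends on the comparator. The mechanism follows from the text alone. The size does not: 0.25-2.25 points in the former placebo group and 0.60-3.75 points in the relugolix groups, both against non-responder imputation, rest on assumed no-diary shares, response rates and equal group sizes. Because the analyses are descriptive and shown by pivotal group, the placebo part is confined to one row. It should be corrected, but it does not threaten the study as a whole.

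**What to change.** In Section 7.2.6 and Tables 13, 14 and 15, replace the carried Week 24 status for women with no extension eDiary by non-responder at Week 52 and Week 104/EOT, for both the pain and the analgesic parts. This is essential for the former placebo group; applying it to all three groups keeps a single rule. Keep these women in the denominator, in line with the general treatment of missing categories in Section 7.1.1, and report their number by pivotal group beside the rate. Retain the Week 24 carry-over only as a labelled sensitivity analysis.

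The cost is SAP wording, one programming rule and one extra sensitivity table. Responder rates will be slightly lower than under the present rule. Section 1 allows the SAP to be amended before database lock.
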